6.1.1 Tier 2 or 3 Procedure Feasibility

Our expectation is that all participating sites will conduct all Tier 2 and 3 tests and procedures. However, we understand that in practice this may not be the case. Sites that are unable to perform one of the study procedures must follow the CSC notification process outlined in the MOP.

6.1.2 SOP Modification Requests

Procedure-specific SOPs are developed to be consistent with the IRB-approved protocol. These SOPs are written to include all clinical variation permitted by the protocol. Any SOP adjustments that are inconsistent with the currently approved protocol will be submitted for IRB review as an overall protocol amendment before implemented.

Procedures in Tier 3 will only be performed concurrently when clinically appropriate. Complete information regarding how tests will be assigned will be in each assessment's SOP. Tier 2 and 3 procedure eligibility, exclusion criteria, and clinical variance affecting the risk/benefit assessment are found in **Appendix 5**: Tier 2 and 3 eligibility, exclusion criteria.

6.2 Characteristics of the Study Population

Number of Subjects: 14,880 subjects with and without existing subject records.

Age of Subjects: 18 years and above.

Racial and Ethnic Origin: Expected overall recruitment by race/ethnicity will be 53% non-Hispanic Whites, 16% non-Hispanic Blacks, 27% Hispanic/Latinx, and 4% Asian Americans, Native Hawaiians, Pacific Islanders, American Indians, and Native Alaskans with equal distributions between male and female populations.

[figure not shown]
Severity of Illness: Targeted distribution will be 25% hospitalized for COVID-19 infection; 75% not hospitalized.

Pregnancy status: Targeted enrollment will be 1,867 infected and 583 uninfected at the time they were pregnant.

6.3 Recruitment and Retention

6.3.1 Recruitment Strategy and Procedures

Recruitment of people with and without SARS-CoV-2 infection will be stratified to ensure adequate representation by sex and race/ethnicity as described in section 6.2. For patients with SARS-CoV-2 infection recruited during or after infection, priority will be placed on recruiting patients from lists of SARS-CoV-2 infected patients to ensure that (a) potential patients were identified prior to study enrollment to minimize bias associated with self-referral, and (b) enrollment response rates can be generated from known denominators. If lists are large, recruitment can be phased using random sampling and adequate "working of recruitment lists" to maximize generalizability. Attempts will be made to include a diversity of

sites of care (e.g. not only from a post-COVID clinic or only from patients cared for in academic medical centers) and severity of illness (i.e. not only from hospitalized patients). For patients without SARS-CoV-2 infection, patients will be randomly sampled and recruited from known lists of potential study subjects in similar communities, demographics, and sites of care as those being recruited into the SARS-CoV-2 positive cohort. Recruitment will be stratified to match the SARS-CoV-2 positive group in terms of racial/ethnic diversity, index time point, and proportion of patients not hospitalized, hospitalized but not in the intensive care unit, and those hospitalized in the intensive care unit.

For patients enrolled after acute infection, preference should be given to those who have data and/or biospecimens collected before or during the acute phase available to the investigators, though efforts should still be made in such cases to recruit an unbiased sample of such patients (for instance, by oversampling this group for underrepresented minority patients or those in communities not already well-represented in the cohort).

If the subject has provided prior consent to be contacted for research at their study site institution, the site study team may create a query in the local EHR system to identify potential subjects based on study entry criteria (age and history of prior diagnosis or testing related to COVID-19). Institutions may also partner with local health departments to obtain complete case lists of people with positive tests in a geographic area. A secure email will be sent to potential subjects to solicit interest in the study, with instructions to contact the study team if interested in participating. This email will be provided to the IRB for review and approval before use in the study. Once contacted by the potential subject, the study Principal Investigator or designated study staff members will provide additional IRB-approved information to the subject as described below and may schedule a study visit. The EHR query or public health department query may be repeated for the duration of the 4-year study. All query responses will be de-identified and retained per section 14.2. A waiver of authorization will be in place at participating sites so study teams can review patient medical records to identify potential subjects who meet eligibility criteria.

[figure not shown]
If a subject requests information regarding opting out of further recruitment for all research, subjects will be directed to site Principal Investigator or designated study team member.

Additional information sent to or available to subjects prior to enrollment may include videos, slide presentations, pamphlets, or website information that provide a general overview of the study and/or more details about the informed consent form. Subjects may view these materials prior to in-person discussion. All materials will be submitted to the IRB for approval prior to their use. Any recruitment information sent by email will utilize a secure encrypted email platform. Once potential subjects have been identified, the study team may need to notify the treating physician that they have patients eligible to participate.

If notification to the treating physician is necessary, one or more of the following methods will be used to notify the treating physician:

- 1. The treating physician will be given a list, advertisement, letters or oral script to use when contacting potential subjects
- 2. The treating physician and site Principal Investigator will send a letter to all potential subjects (letter must have both names)
- 3. If the treating physician agrees, the study team will directly contact potential subjects on behalf of TP by letter, phone, email, or an electronic medical record patient portal.

Once contact is made, approved recruitment language will be used to communicate the reason they are being contacted and subjects will be asked if they are interested in participating in this specific study. Should the potential subjects agree, the study team will provide the subjects with information regarding the next steps for participation.

Social media platforms, websites, conventional mass media (radio and print publications), flyers or other advertising may also be used for recruitment purposes. All recruitment materials or text for any of these platforms will be submitted to the IRB for approval prior to use.

6.3.2 Retention Strategy

Participant retention may be promoted by providing educational materials related to PASC symptom management, through newsletters or other periodic outreach, through personalized periodic contact (e.g., birthday greetings), by rollout of a mobile application, by creation of a patient web portal to provide access to study personnel for questions, and by using feedback received from participants to enhance participant experience. Additional efforts may be made to minimize attrition: 1) reminder calls for assessments, rescheduled if missed; 2) maintaining contact information (e.g., updating at each contact, obtaining alternate contacts, re-connecting in primary care), and maintaining ongoing contact with all participants during the study. All materials used for participant retention will be provided to the IRB for review and approval before use in the study.

Contacts with participants may include reminders for completion of study surveys, reminders for study appointments, a post-visit thank-you card or call, a newsletter, a birthday or greeting card, and a holiday or end-of-year card. We aim to design both culturally and religiously appropriate contact documents. Therefore, these contacts will be initiated by each site and will be conducted in the language of choice of the participant. In addition, because some religions (e.g., Jehovah's Witnesses) may not celebrate birthdays or holidays, specialized cards will be designed to accommodate these participants. Newsletters and cards sent to RECOVER respondents will be reviewed for health literacy to ensure comprehension among participants of varying literacy levels.

[figure not shown]
Participant response burden may be monitored in real-time during the study. If burden is found to be excessive, it may be reduced by altering the overall study data collection strategy, such as by increasing the interval of assessments to 6 months instead of 3 months; reducing the number of data elements collected (eliminating rare symptoms); pre-filling prior responses to reduce data entry time for patients; tightening criteria for Tier 2 and Tier 3 data collection; increasing the availability of home-based Tier 2/3 assessments; and/or increasing participant reimbursement. All such modifications will be approved by the IRB before implementation study wide. Individuals at risk of withdrawing from the study because of burden may, on a case-by-case basis, be offered: the option to skip an interval assessment (e.g. if traveling); the option to skip a survey instrument that is not the PASC symptom survey; the option to increase the interval of assessments to 6 months; home-based Tier 2/3 assessments where feasible; or, if no other strategy is acceptable, the option to return for a final assessment only.

Recruitment and retention data will be monitored on an ongoing basis to compare target versus actual recruitment rates by site (stratified by race/ethnicity, hospitalization status and acute infection at enrollment); compare the number of expected surveys completed and biospecimens collected to target; and to review participant retention reports indicating the number of participants active, completed, and lost to follow-up.

7 Study Enrollment and Withdrawal

7.1 Inclusion Criteria

- Patients will be eligible for inclusion if they are at least 18 years of age and have reached the age of majority in their state of residence.
- Infected individuals must have suspected, probable, or confirmed SARS-CoV-2 infection as defined by WHO criteria within 36 months of enrollment, or positive SARS-CoV-2 infection-specific antibody testing, to meet inclusion criteria.
- Participants must be willing to generally comply with the overall protocol (e.g. cannot agree to
 participate only for survey collection) and must expect to be available for the duration of the study.

Adults with suspected SARS-CoV-2 infection

An adult qualifies as having suspected SARS-CoV-2 infection if meeting criteria a, b or c below:

a) Patients who meet the following clinical criteria plus one of the epidemiological criteria: Clinical criteria: Acute onset of fever and cough OR acute onset of any three of more of the following signs or symptoms: fever, cough, general weakness/fatigue, headache, myalgia, sore throat, coryza, dyspnea, anorexia/nausea/vomiting, diarrhea, altered mental status. Note: Signs separated with a slash (/) are counted as one sign, in which the slash means "OR" (i.e., participants may have anorexia and/or nausea and/or vomiting; any combination of these symptoms counts as one of three symptoms needed to meet clinical criteria).

Epidemiological criteria:

- Residing or working in an area with a high risk of transmission of virus: closed residential settings, humanitarian settings such as camp and camp-like settings for displaced persons; anytime within the 14 days before symptom onset; or
- ii. Residing or travel to an area with community transmission* anytime within the 14 days before symptom onset; or
- iii. Working in any health care setting, including within health facilities and within households or within the community; anytime within the 14 days before symptom onset.

*Note: For purposes of this protocol, we define "community transmission" as any county with at least substantial community transmission according to the CDC definition (50 or more cases per 100,000 in the past 7 days). If the participant has traveled to or from another country, use the most granular data available to determine transmission in that area. Historical data about community transmission levels can be found in the MOP.

- b) A patient with severe acute respiratory illness: (acute respiratory infection with history of fever or measured fever of ≥38C°; and cough; with onset within the last 10 days; and requires hospitalization).
- c) A person with a positive SARS-CoV-2 Antigen-RDT who is asymptomatic or meets some but not all clinical or epidemiologic criteria.

Note: A patient who meets criteria for suspected SARS-Cov-2 infection who had a negative test at the time does NOT qualify as an infected case.

Adults with probable SARS-CoV-2 infection

An adult qualifies as having probable SARS-CoV-2 infection if meeting any one of a-d below:

[figure not shown]
- a) A patient who meets clinical criteria for suspected SARS-CoV-2 AND is a contact of a probable or confirmed case or linked to a COVID-19 cluster;
- b) A suspect case with chest imaging showing findings suggestive of COVID-19 disease;
- c) A person with recent onset of anosmia (loss of smell) or ageusia (loss of taste) in the absence of any other identified cause;
- d) Death, not otherwise explained, in an adult with respiratory distress preceding death AND was a contact of a probable or confirmed case or linked to a COVID-19 cluster (Not applicable to the RECOVER adult protocol)

Note: A patient who meets criteria for probable SARS-Cov-2 infection who had a negative test at the time does NOT qualify as an infected case.

Adults with confirmed SARS-CoV-2 infection

An adult qualifies as having confirmed SARS-CoV-2 infection if meeting any one of a-d below:

- a) Any person with a positive Nucleic Acid Amplification Test (NAAT) OR positive SARS-CoV-2 antibody test*;
- b) Any person with a positive SARS-CoV-2 Antigen-RDT (including home-administered rapid test) AND meeting either the probable case definition or suspect criteria A OR B;

- c) An asymptomatic person with a positive SARS-CoV-2 Antigen-RDT (including home-administered rapid test) who is a contact of a probable or confirmed case;
- d) Any person with a positive SARS-CoV-2 nucleocapsid protein antibody test OR a positive SARS-CoV-2 spike protein antibody test IF not vaccinated.

*This protocol modifies the WHO criterion a to add detectable SARS-CoV-2 antibody as a qualifying test

Adults with no SARS-CoV-2 Infection

- Does not meet WHO criteria for a suspected, probable, or confirmed case of SARS-CoV-2 infection, AND
- Has negative NAAT SARS-CoV-2 testing from a respiratory specimen performed at the time of enrollment/screening AND
- Has a negative SARS-CoV-2 nucleocapsid protein antibody and spike protein antibody test (spike only if not vaccinated) performed at the time of enrollment, AND
- Lives in the same communities or recruited from the same sources as those in the SARS-CoV-2 infected cohort.

Note: uninfected individuals may participate independent of their vaccination status

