8.1 Overview of Study Schedule

Data will be collected at baseline and then following the study schedule, which starts at time of first infection for those enrolled during first infection or after their first infection without an active infection at time of enrollment; at time of reinfection if enrolled during an acute infection; or at time of negative COVID-19 test, for those who are uninfected. Uninfected pregnant individuals will begin the study schedule on their delivery date. See **Table 3**. Collection will be tiered such that all enrolled patients will undergo Tier 1 data collection, and those with abnormal findings on Tier 1 collection may progress to more intensive, invasive, or costly Tier 2 and Tier 3 data collection. We anticipate that approximately 30% of participants will undergo each Tier 2 test and a maximum of 20% of enrollees will undergo each Tier 3 test for any given symptom, including both those with relevant symptoms and a random sample of 5.6% of SARS-CoV-2 infected and 11.4% of uninfected subjects without relevant symptoms. All patients will undergo at least one in-person visit annually, which can be provided at home if provisions are made for home blood and biospecimen collection.

Table 3: Index date and study schedule date, by enrollment type

Enrollment Category	Index Date	Study Schedule Start Date	
Acute Infected (First Infection)	First positive SARS-CoV-2 test	First positive SARS-CoV-2 test	
	result date or, if test not	result date or, if test not	

	available, date of COVID symptom onset	available, date of COVID symptom onset
Acute Infected (Reinfected)	First positive SARS-CoV-2 test result date or, if test not available, date of COVID symptom onset	Most recent positive SARS- CoV-2 test result date or, if test not available, date of COVID symptom onset
Acute Uninfected	Qualifying negative SARS-CoV-2 test result date	Qualifying negative SARS-CoV-2 test result date
Post-Acute Infected	First positive SARS-CoV-2 test result date or, if test not available, date of COVID symptom onset	First positive SARS-CoV-2 test result date or, if test not available, date of COVID symptom onset
Post-Acute Uninfected	Qualifying negative SARS-CoV-2 test result date. For pregnancy sites only , index date is the prior delivery date	Qualifying negative SARS-CoV-2 test result date. For pregnancy sites only , index date is the prior delivery date

Home Visits

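### Confirmed-infection criterion (a) accepts any positive SARS-CoV-2 antibody test, so the vaccination limit on spike antibody in criterion (d) has no effect

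*Protocol*

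**What the plan says.** All of the eligibility text is in Protocol section 7.1.

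- **Joining rule:** "An adult qualifies as having confirmed SARS-CoV-2 infection if meeting any one of a-d below". One criterion is enough.
- **Criterion (a):** "Any person with a positive Nucleic Acid Amplification Test (NAAT) OR positive SARS-CoV-2 antibody test". The footnote reads "This protocol modifies the WHO criterion a to add detectable SARS-CoV-2 antibody as a qualifying test". Neither names an antigen or mentions vaccination.
- **Criterion (d):** "Any person with a positive SARS-CoV-2 nucleocapsid protein antibody test OR a positive SARS-CoV-2 spike protein antibody test IF not vaccinated".
- **General inclusion bullet for infected participants:** WHO-defined infection within 36 months of enrollment, "or positive SARS-CoV-2 infection-specific antibody testing, to meet inclusion criteria".
- **Uninfected participants:** they must not meet the WHO case criteria and must have negative antibody tests, with spike counted on the terms "spike only if not vaccinated". A note adds that uninfected people may take part whatever their vaccination status.

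Section 8.1, Table 3, sets the index date for infected participants as "First positive SARS-CoV-2 test result date or, if test not available, date of COVID symptom onset". It does not say which kinds of test count.

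**The concern.** Criteria (a) and (d) sit in one list and give opposite answers for a vaccinated person whose only positive result is spike antibody: (d) refuses that result as evidence of infection and (a) accepts it. Because one criterion suffices, (a) wins.

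Infected versus uninfected is the exposure in hypotheses 1b to 1e (section 12.1) and in the first row of Table 7. Never-infected people in the infected cohort would pull every infected-uninfected contrast toward zero.

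A secondary issue concerns time zero. Table 3 does not restrict the test type, so someone who qualifies by antibody alone may be indexed at the serology date. For a truly infected person, that could place an older infection at month 0 of analyses indexed by time since infection.

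**Working it through.** **Step 1: the rule applied to one person.** Take a vaccinated, never-infected person with no qualifying illness and a negative NAAT, who is spike-positive and nucleocapsid-negative.

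| Section 7.1 text | Result |
|---|---|
| Confirmed (a) and footnote | Met: an antibody test is positive |
| Confirmed (d) | Not met: vaccinated, nucleocapsid-negative |
| Any one of a-d | Confirmed infected, through (a) |
| General bullet, infection-specific antibody branch | Not met |
| Uninfected, serology bullet | Passed: spike is set aside |
| Uninfected, first bullet | Failed if WHO criteria means the protocol's modified list; passed if it means the unmodified WHO list |

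Every result that satisfies (d) is a positive antibody test and so satisfies (a). Criterion (d) therefore changes no one's classification. The general bullet does not block entry through (a), because its antibody wording is an alternative to a confirmed case and not a condition on it.

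**Step 2: reproduce the planned figure.** Inputs are 12,200 infected and 2,680 uninfected (section 1), and a PASC risk of 25% in infected with a minimum detectable difference of 3.50% (Table 7, first row). The protocol states neither alpha nor power. A pooled two-proportion test at two-sided alpha 0.01 and 90% power gives 3.49%. It also gives 6.84% for the 25% subgroup (stated 6.80%), 4.10% for the pregnancy row and 3.90% for the risk-factor row, both as stated. This pair is inferred and not unique: alpha 0.025 with 95% power gives 3.51%.

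**Step 3: dilution.** Suppose a share f of the infected cohort was never infected and has the uninfected risk of 25% − 3.5% = 21.5%. Then

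observed infected risk = (1 − f) × 25% + f × 21.5%

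observed difference = (1 − f) × 3.5 points.

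Power = Φ[(d − 2.576 × SE₀) / SE₁], where d is the observed difference, SE₀ uses the pooled proportion and SE₁ the two separate proportions. At f = 0:

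- pooled proportion = (12,200 × 0.25 + 2,680 × 0.215) / 14,880 = 0.2437
- SE₀ = √[0.2437 × 0.7563 × (1/12,200 + 1/2,680)] = 0.00916
- SE₁ = √[0.25 × 0.75/12,200 + 0.215 × 0.785/2,680] = 0.00885
- (0.035 − 2.576 × 0.00916) / 0.00885 = 1.29, so power is 90%.

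The documents give no value of f. The rows below are assumptions that show how the result scales.

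| f (assumed) | People, of 12,200 | Observed difference (points) | Power, alpha 0.01 |
|---|---|---|---|
| 0 | 0 | 3.50 | 90% |
| 1% | 122 | 3.47 | 89% |
| 5% | 610 | 3.33 | 86% |
| 10% | 1,220 | 3.15 | 82% |
| 20% | 2,440 | 2.80 | 70% |

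At two-sided alpha 0.05 the same difference has 97% power at f = 0 and 94% at f = 10%. The proportional shrinkage of the estimate does not depend on alpha.

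**The case against.** The strongest defence is that (a) is loose drafting around a rule that is clear elsewhere. The general bullet requires "positive SARS-CoV-2 infection-specific antibody testing", (d) excludes spike after vaccination, and the uninfected rule does the same. Since the footnote says antibody is not part of WHO criterion a, one can argue that antibody-only entry has to pass through the infection-specific branch, which vaccine-induced spike does not satisfy. That reading is possible and shows the intent. It does not remove the conflict: the section's own list of confirmed criteria includes antibody without limit, and nothing gives (d) priority over (a).

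The defence is right that the practical effect may be small. Section 6.3.1 gives priority to recruiting from lists of infected patients, and Appendix 2 lists enrollment serology for uninfected controls, for whom spike is set aside if vaccinated. The manual of operations may also apply (d), but it is not shown.

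Three stronger readings are tempting and not supported:

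- **That vaccinated people are shut out of the controls.** This holds only for spike-positive people, and only if the modified definition governs the first uninfected bullet. The protocol expressly allows vaccinated controls.
- **That vaccine-only entrants escape the 36-month window.** Someone entering as a confirmed case is still under it. The branch without a window requires infection-specific antibody.
- **That a large share of the cohort is affected.** No figure in the protocol supports 10% or 20%.

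**Conclusion.** The rule is wrong as written. Criterion (a) and its footnote cancel the vaccination limit in (d) and contradict two other parts of section 7.1. This is an error in the definition of the main exposure, which belongs in the protocol, and not a detail left to the SAP.

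The size is the factor (1 − f) on each infected-uninfected risk difference, assuming that misclassified people carry the uninfected risk. The effect on power is slight if f is near 1% and material only if f is much larger. The power figures also rest on an inferred alpha. A reader might infer that never-infected people have in fact been enrolled as infected; the protocol permits this on a literal reading but does not show that it happened.

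The time-zero point is secondary and is an inference, since Table 3 neither names nor excludes antibody tests. Correcting (a) would not settle it, because (d) still admits antibody-only cases. Whether such cases belong in time-indexed analyses is an analysis-set decision that the SAP may already address.

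**What to change.** 1. In section 7.1, delete antibody from criterion (a) and its footnote, or limit it there to the terms of (d). Either change makes the general bullet, the confirmed criteria and the uninfected criteria agree. State also whether the first uninfected bullet refers to the WHO list or to the protocol's modified list.
2. Identify participants who qualified only by spike antibody after vaccination, and reclassify them. Appendix 2 already lists diagnosis method, vaccination details, and spike and nucleocapsid antibodies. Whether the antigen of an outside qualifying test was recorded cannot be seen from the protocol. Report the number found, which replaces the assumed f.
3. In Table 3, state how the index date is set for antibody-only cases, and flag them for a sensitivity analysis wherever time since infection is the axis.

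The cost is a short amendment and a query on data that the protocol already collects, plus the loss from the infected cohort of whatever number the query finds.
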